## 17.4. Qualitative assessments

Previous studies have shown that qualitative work on outcomes can be helpful in interpreting trial findings from a participant's point of view. During FORENSIC-UK follow-up, interviews will be undertaken by the QRI researcher with up to 25 participants who consent to the Information Study, purposively sampled to include those reporting good and poor outcomes based on the ODI score from each trial arm to provide participant perspectives to understand nuances of outcomes.

## 17.5. Withdrawal of participants

## Withdrawal of consent by the participant

Withdrawal of consent means that a participant has expressed a wish to withdraw from the study altogether or from certain aspects of the study only. The type of withdrawal will be collected on the CRF labelled 'Withdrawal'. It is important that every effort is made to encourage participants, including those participants who do not receive/complete their allocated treatment, to complete follow-up questionnaires, and attend for their CT scan (in those who have LFS) to avoid bias in the analysis of the results.

Participants may also be withdrawn from the study (or aspects of the study) by their clinician if they believe the participant needs to be withdrawn.

The Withdrawal CRF should be completed to document the reasons for withdrawal and state who the decision to withdraw was made by. Discussions and decisions regarding withdrawal should be documented in the participant's medical notes. Investigators should continue to follow- up any SAEs and should continue to report any SAEs to resolution in the CRF in accordance with the safety reporting section.

Where a participant expresses a wish to withdraw from the study, the research team will determine which aspect(s) of the study the participant wishes to withdraw from.

The aspects of the study that the participant may request to withdraw from are as follows:

- No longer willing to receive study intervention.
- No longer willing to complete study questionnaires.
- No longer willing to take part in the qualitative interviews as part of the Information Study.
- No longer willing to receive study-related communications.
- No longer willing to attend study visits.
- No longer willing to have study CT scans.
- No longer willing to be contacted by the research team to obtain CRF data
- No longer willing to be contacted by research team to obtain outcome data.
- No longer willing for routine data from health data providers e.g. NHS England, to be provided to the study.
- No longer willing for trial data to be shared with the British Spine Registry
- No longer willing to participate in any of the above aspects (full withdrawal)

Where a participant wishes to withdraw from all aspects of study participation detailed above this will be recorded on the Withdrawal CRF as full withdrawal.

In addition to participant self-withdrawal, an investigator may decide to withdraw a participant from trial treatment for clinical reasons. Participants will still be asked to participate in the collection of follow-up data. The reason for withdrawal will be recorded on the study withdrawal case report form. Withdrawn participants will not be replaced as we have allowed for possible withdrawals and loss to follow-up in the estimated sample size.

Completion of the Withdrawal CRF by the site research team will trigger a notification to the Study Office. Appropriate action will be taken by the study teams (centrally at the CTU and by the site research team at each participating site) to ensure compliance with the participant's withdrawal request. This may include marking future CRFs as not applicable and ensuring any relevant communications which the participant had consented to receive regarding their participation are no longer sent.

Data collected up to the point of withdrawal will be used/analysed as explained in the PIS, unless the participant specifically requests otherwise.

## **BLINDING AND CODE BREAKING**

Participants and clinicians delivering the interventions will not be blinded to intervention allocation due to the nature of the interventions.

Table 3: provides an overview of the blinding status of all individuals involved in the conduct and management of the study.

Role in study	Blinding status	Additional information
Participants	Not blinded	It is not possible to blind due to the nature of the
		interventions. Participants will be told their treatment
		allocation immediately after randomisation.
Site clinical and	Not blinded	It is not possible to blind due to the nature of the
research staff		interventions. Following randomisation, an email will be
including Principal		sent to the members of the site research team, as
Investigator		applicable, performing the randomisation (as delegated)
		confirming treatment allocation.
Chief	Blinded, except	The Chief investigator will remain blinded to treatment
Investigator(s)	for any SAE	allocation overall (knowledge of treatment allocation is
	causality	limited to participants at their own site). In instances
	assessment.	where serious adverse events are reported, the CIs will
		become unblinded to complete the full causality
		assessment.
Database	Not blinded	The database programmer is responsible for the
programmer		management of RRAMP randomisation system and the
		REDCAP database and will have access to all unblinded
		datasets within both systems.
FORENSIC-UK	Not blinded	Study Management staff within FORENSIC-UK study
Study Management		team will not be blinded to treatment allocations as site
staff within		staff may require support for randomisation, or
FORENSIC-UK study		participants may contact the study team directly. Serious
team		Adverse Event reports will also be handled by the study
		management team which will contain allocation
-		information.
Data Management	Not blinded	Data management staff will have access to the unblinded
		datasets within the study randomisation system and
		database to ensure data quality and undertake central
		monitoring activities.

Table 3: Blinding status of those involved in study	y conduct and management.
---	---------------------------

Study statistician and Senior Study Statistician	Not blinded	The study statistician and senior study statisticians will have access to treatment allocations or data needed for generating the Data Monitoring Committee (DMC) closed reports and the final analysis.
Health Economist	Not blinded	The costs of the two interventions in this trial are considerably different and thus it will not be possible to blind the health economist.
TSC	Blinded	Will review accruing data and safety overall only, not separated by treatment groups. Full details will be specified in the TSC charter.
DSMC	Not Blinded	DSMC will review accruing data and safety by treatment groups. Allocation may be blinded (arm A or B). Full details will be specified in the DSMC charter and DSMC Report template

## 17.6. Code break/ unblinding.

Not applicable for this study.

#### 18. SAMPLES

The study protocol does not require any samples to be taken from study participants.

#### 19. IMAGING

Data will be collected on any MRI, SPECT CT, standing X-Rays and other imaging that has been undertaken in the 12m pre-randomisation.

For participants randomised to the surgery arm they will undergo Image intensification during the surgical procedure.

Standard Computed Tomography (CT) scans for patients randomised to surgery will be carried out at the 24-month follow-up time point as part of the fidelity assessment. The clinical team at the local site will review and complete a CRF to indicate whether spinal fusion was achieved.

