#### 9.2. Primary and secondary objectives and outcome measures

The primary outcome is the Oswestry Disability Index (ODI), a validated LBP physical function disability score, at 24 months (also measured at 6 & 12 months). The ODI is well validated and a commonly used outcome measure in LBP RCTs including surgery and contains 10 items that assess domains including personal care, walking, standing and sleeping.

Secondary outcomes include LBP severity (Numerical Rating Scale), measured using monthly SMS data or by email or paper options dependant on participant preference (over 24 months). We will also collect participant reported outcome measures reported via questionnaires at 6, 12 and 24 months. The participant questionnaires include: quality of life (EQ-5D-5L), depression (PHQ8), fear avoidance beliefs (TSK), pain self-efficacy (PSEQ), work outcomes (days-off-work), comparison of back pain from entering the study to timepoint of questionnaire using Global Perceived Effect Scale (GPE), healthcare use (NHS and non-NHS including concurrent treatments ie: analgesia) and treatment satisfaction measured at 24 months follow-up with scoring 0-10 (with 10 being very satisfied with treatment).

Further secondary outcome measures will be collected throughout the 24 months using specially designed CRF's to be completed by clinicians and researchers regarding surgery, Best Conservative Care (BCC), Surgery complications (intra and post operative), further surgery including re-admission, Fusion Failure (LFS participants only), BCC complications.

Objective	Outcome measure	Time point(s) of evaluation of this outcome measure (if applicable)
1. To test for superiority of	Primary:	24 months (also measured at 6
lumber fusion surgery (LFS)	LBP-related physical function	& 12 months)
versus BCC on disability	using the Oswestry Disability	
(physical function) in	Index (ODI version 2.1b)	
patients with persistent		
lower back pain (LBP)		
	Secondary:	
2. To investigate the cost-		
effectiveness of LFS	LBP severity (Numerical	
compared with best	Rating Scale) monthly – post	
conservative care (BCC)	randomisation	
	Participant reported	
	outcomes	

	measured at 6m, 12m and	
	24m post randomisation:	
	1. Quality of Life: EQ-5D-5L	
	2. Pain Self-efficacy	
	Questionnaire (PSEQ)	
	3. Patient Health	
	Questionnaire (PHQ8)	
	4. Tampa Scale of	
	Kinesiophobia (TSK)	
	5. Global Perceived Effect	
	Scale (GPE)	
	6. Healthcare Resources	
	Use	
	7. Work status	
	8. Treatment Satisfaction	

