#### 10.9. Central review procedures

Not applicable for this study.

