#### 13. STUDY INTERVENTION AND COMPARATOR

#### 13.1. Lumbar Fusion Surgery [LFS] & post-operative care (intervention)

For participants randomised to LFS all commonly accepted fusion methods and graft options within the NHS will be permitted as; 1) there is no evidence of superiority for one method of LFS over another; 2) the approach will enable greater generalisability and external validity for change in practice should LFS be superior, and 3) it will facilitate recruitment of sites/surgeons (and therefore participants) to the trial, many of whom may undertake varying approaches to LFS. All methods permitted for the trial have been reviewed and agreed by the FORENSIC-UK Clinical Advisory Group (FORENSIC-UK CAG) and approved at the British Association of Spinal Surgeons (BASS) conference 2024.

The FORENSIC-UK CAG felt strongly that bone morphogenetic protein (BMP)which may be used in spinal fusion procedures is a confounder and should be excluded. Reflecting the pragmatic nature of this trial, overall level of experience of the operating surgeon will not be an inclusion factor but all surgeons performing LFS in the trial will be required to be familiar with the techniques and equipment used at their respective site. Inter-operative data will be collected on the surgical

approach to the LFS (anterior, posterior, lateral, level(s)) and the types of implants and bone graft used.

For Lumbar fusion surgery (LFS), i.e. 1 or 2 level LFS, either posterolateral or interbody, (other than excluding BMP and mixed fusion procedures [i.e. fusion with decompression, fusion with disc replacement at the same of different levels]), there are no limitations (within accepted methods) for implants, bone grafts or surgical approach, given the evidence that none are superior. LFS also includes intra/postoperative x-rays, usual review appointment (which may be via telehealth) for example at 6-8 weeks and usual post-operative care. All participants undertaking LFS will have a CT Scan at 24 months follow-up to establish fused/not fused. We will finalise mandatory/optional/prohibited components, including how to record, and check fidelity of the LFS in the internal pilot phase. We will also collect data on the operation specifics i.e. date of surgery and any intraoperative complications.

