#### Fidelity of the LFS arm

Issues of adherence and fidelity are more straightforward for LFS (there are no grades of adherence to the surgery), but a different set of fidelity issues exist. A surgical procedure CRF will be included to record what was done at operation. It is also important to ascertain whether lumbar bony fusion has occurred or not, especially for interpretation of trial results. A follow-up CT scan for those who have LFS in the trial, at 24 months post-date of randomisation, will provide these data.

The assessed fidelity will be fed back to sites for the duration of the trial, including evaluation of whether intervention fidelity changes during the trial. This is in keeping with the revised guidelines from MRC on complex healthcare interventions and similar approaches have been utilised elsewhere.

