## 24.5. Access to Data

To ensure compliance with regulations, direct access will be granted to authorised representatives from the Sponsor and host institution to permit study-related monitoring, audits and inspections. The data submitted by study participants directly via the clinical database REDCap (i.e. electronic participant reported outcomes) will also be made available to the participating site that recruited the participant; this is detailed within the PIS so that participants are aware of who will have access to this data.

Members of the study team will only be able to access data that they need to, based on their roles and responsibilities within the study.

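### Fusion status on the 24-month CT is judged by the unblinded local clinical team, and nothing prevents the operating surgeon from grading their own operation (minor)

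*Protocol*

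**What the plan says.** Section 13.1 sets the measurement: "All participants undertaking LFS will have a CT Scan at 24 months follow-up to establish fused/not fused". Section 19 names who decides: "The clinical team at the local site will review and complete a CRF to indicate whether spinal fusion was achieved". Section 10.9, on central review, reads "Not applicable for this study".

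On blinding, the protocol says: "Participants and clinicians delivering the interventions will not be blinded to intervention allocation due to the nature of the interventions". Table 3 likewise lists site clinical and research staff, including the Principal Investigator, as not blinded.

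On the role of the result, the text of section 9.2 includes it among the further secondary outcome measures: "further surgery including re-admission, Fusion Failure (LFS participants only), BCC complications". The outcome table in that section does not list it, and sections 17.3 (CT scan appointment) and 19 describe the CT as part of the fidelity assessment. Section 13.4 adds: "It is also important to ascertain whether lumbar bony fusion has occurred or not, especially for interpretation of trial results".

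On access to outcomes, section 24.5 says that data which participants submit directly through REDCap "will also be made available to the participating site that recruited the participant". The same section limits each team member's access to what their role requires.

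**The concern.** Some CT scans will be equivocal. A reader who knows how the participant is doing may resolve those scans towards the clinical picture: fused when the participant has done well, not fused when they have done badly. A reader who performed the operation also has a stake in the answer. Section 19 permits both, because it names only the local clinical team. The result is framed as fused or not fused, so the protocol gives no category for a scan that cannot be called.

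Two things are at stake. The first is the fusion rate reported for the surgery arm. The second is any explanation of the trial result that leans on fusion status, a use section 13.4 anticipates. If symptoms have entered the reading, putting a null result down to failed fusion, or crediting a positive one to solid fusion, is partly circular.

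**Working it through.** **Is the choice fixed in the protocol?** Section 13.1 leaves to the internal pilot how the fidelity of surgery is recorded and checked, so categories and form-completion rules may still be settled there. Section 19 already fixes who judges, and section 10.9 rules out a central reading. No section excludes the operating surgeon or asks for a reader unaware of the participant's outcome.

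**Which results can be affected?** Fusion is read only in participants who had surgery. The primary analysis in section 22.3 compares ODI between randomised arms and does not use fusion status. The sensitivity analyses there (complier average causal effect, time from intervention, area under the curve, per-protocol, type of conservative care, missing data) do not use it. The subgroups named in section 22.5 (levels, baseline ODI category, delayed intervention) do not either, although the full list is left to the SAP. What remains exposed is the descriptive fusion rate and informal interpretation.

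**How large could a distortion be?** The protocol plans no such comparison, so this only illustrates the mechanism.

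Inputs from section 22.2: ODI SD 18; 135 per arm with up to 20% loss, so 135 × 0.8 = 108 scans. The plan's own sample size reproduces: a two-sided 5% t-test for 8 points with SD 18 at 90% power needs 108 per arm, and 108 / 0.8 = 135, or 270 in total.

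Assumed, not in the documents:
- true non-union p = 15%, unrelated to ODI
- equivocal share e = 20%
- a fraction s of equivocal scans is read by symptoms, the worst third on ODI being called not fused and the rest fused
- all other scans are read correctly

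Let k = e × s. The proportion called not fused is P = (1 − k)p + k/3. The worst third of a normal distribution with SD 18 lies on average 18 × 0.3636 / (1/3) = 19.63 points above the mean. The spurious gap (not fused minus fused) is

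gap = (k/3 × 19.63) / [P(1 − P)]

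| s | k | P | Gap (ODI points) |
|---|---|---|---|
| 0 | 0 | 0.150 | 0 |
| 0.10 | 0.02 | 0.154 | 0.131 / 0.1301 = 1.0 |
| 0.25 | 0.05 | 0.159 | 0.327 / 0.1338 = 2.4 |
| 0.50 | 0.10 | 0.168 | 0.654 / 0.1400 = 4.7 |
| 1.00 | 0.20 | 0.187 | 1.309 / 0.1518 = 8.6 |

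Simulation with 108 scans agrees within Monte Carlo error (about 2.5 points at one quarter, 4.5 to 4.7 at one half, 8.6 to 8.7 at all). A t-test of fused against not fused would reject at 5% in about 6% of trials at s = 0.10, 9% at 0.25, 16% to 18% at 0.50 and 50% to 51% at 1, against 5% with an unbiased reading.

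At s = 1, varying non-union over 10% to 25% and equivocal scans over 10% to 30% moves the gap between 3.4 and 13.9 points. At any setting it goes to zero as s goes to zero.

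The fusion rate moves less. Under this rule apparent non-union rises from 15% to at most 18.7%. If instead every equivocal scan were called fused, it would fall to 0.8 × 15% = 12%. The direction therefore depends on the reader's leaning.

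**The case against.** The strongest reply is that the trial's answer is untouched. Fusion is read in one arm only and no fused versus not-fused ODI analysis is specified. This stands, and it limits the point to a minor one. A reader might infer from a gap near 8 points, the size of the target difference, that the trial's conclusion is at risk. The documents do not support that: the target difference belongs to a randomised contrast that this reading does not enter.

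Second, every input to the illustration apart from the SD and the number of scans is assumed, and the symptom-led share drives the result. This also stands, so the range has to start at zero.

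Third, fusion's standing as a secondary outcome rests on one phrase in the text of section 9.2, since the outcome table omits it and the CT is described as fidelity assessment. This is correct. Section 13.4 nevertheless gives fusion status an interpretive role, and fidelity data also need an unbiased reading.

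Fourth, a reader might infer from section 24.5 that whoever grades the CT sees the 24-month ODI. The text does not show this. Access is limited by role, it covers only data submitted directly in REDCap, and paper questionnaires go to the Trial Office (section 17.3). Nor does the protocol say that the operating surgeon grades the scan. Both are permitted or possible, not stated, and symptom-led reading is a risk rather than a documented fact.

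Finally, the pilot may settle the recording rules. It may, but section 19 has already said who judges, and an analysis plan cannot undo a reading made with symptoms in view.

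**Conclusion.** The point holds as a minor one. The protocol gives the fusion decision to an unblinded local team, without central review and without excluding the operating surgeon, while assigning the result a role in interpreting the trial. This could bias the reported fusion rate and any informal account of the trial result by fusion status. It cannot bias the randomised ODI comparison.

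If fused and not-fused participants were compared on ODI, the spurious gap would run from 0 through about 2.5 to about 8.6 points as the symptom-led share of equivocal scans goes from none through one quarter to all. That rests on assumed values of 15% non-union and 20% equivocal scans and on the worst-third rule. It shows that the mechanism can matter and is not an estimate of what will happen here.

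**What to change.** In section 19, state that the fusion form is completed by a site clinician who did not perform the operation and who does not consult the participant's follow-up ODI or symptom record when grading. Where a formal radiology report of the 24-month CT is issued, the form is completed from that report. This must be conditional, because no section says that one is issued for every scan. Record fused, not fused or uncertain, and keep uncertain as its own category in reporting.

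The cost is wording in section 19 and one extra category on the form. No extra scan or central panel is needed, and a site clinician already completes this form. The downside is that some results will be uncertain and some forms will need a query. A non-operating clinician may still know the participant from clinic, so the change reduces the risk without removing it.

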#### 20. SAFETY REPORTING

#### 20.1. Safety reporting period

Safety reporting for each participant will begin from the first point of administration of the intervention i.e. lumbar fusion surgery or best conservative care and will end when the participant has reached their final main follow-up time point, at 24 months post-randomisation (including period for CT scan at 24 months for participants who have undergone Lumbar Fusion Surgery).

#### 20.2. Definitions

These are listed in Table 4.

#### Table 4: Safety reporting definitions

An adverse event (AE)	Any untoward occurrence in a trial participant. An AE can therefore be any unfavourable and unintended sign (including an abnormal laboratory finding, for example), symptom or disease temporarily associated with study procedures, whether or not considered related to the procedures.
Related Adverse	An event that resulted from administration of any of the research
Event	procedures
Serious Adverse	An AE that:
Event (SAE)	
 
results in death
 
is life-threatening
 
requires hospitalisation or prolongation of existing hospitalisation
 
results in persistent or significant disability or incapacity
 
is a congenital anomaly or birth defect
 
is otherwise considered medically significant by the Investigator
 

Unexpected Related Serious Adverse Event	A serious adverse event related to the study (i.e. resulted from administration of any of the research procedures) and is unexpected (not listed in the protocol as an expected occurrence).

 Participant was at risk of death at the time of the event; it does not refer to an event which hypothetically might have caused death if it were more severe

 Medical events that may jeopardise the participant or may require an intervention to prevent one of the above characteristics/consequences.

A distinction is drawn between serious and severe AEs. Severity is a measure of intensity whereas seriousness is defined using the criteria above. Hence, a severe AE need not necessarily be serious.

